7.6. Special Situations Reports

7.6.1. Definitions of Special Situations

Special situation reports include all reports of medication error, abuse, misuse, overdose, reports of adverse events associated with product complaints, occupational exposure with an AE, pregnancy reports regardless of an associated AE, and AE in an infant following exposure from breastfeeding.

Medication error is any unintentional error in the prescribing, dispensing, or administration of a medicinal product while in the control of the health care provider, subject, or consumer.

Abuse is defined as persistent or sporadic intentional excessive use of a medicinal product by a subject.

Misuse is defined as any intentional and inappropriate use of a medicinal product that is not in accordance with the protocol instructions or the local prescribing information.

An overdose is defined as an accidental or intentional administration of a quantity of a medicinal product given per administration or cumulatively which is above the maximum recommended dose as per protocol or in the product labelling (as it applies to the daily dose of the subject in question). In cases of a discrepancy in drug accountability, overdose will be established only when it is clear that the subject has taken the excess dose(s). Overdose cannot be established when the subject cannot account for the discrepancy except in cases in which the investigator has reason to suspect that the subject has taken the additional dose(s).

Product complaint is defined as complaints arising from potential deviations in the manufacture, packaging, or distribution of the medicinal product.

Occupational exposure with an AE is defined as exposure to a medicinal product as a result of one's professional or non-professional occupation.

7.6.2. Instructions for Reporting Special Situations

7.6.2.1. Instructions for Reporting Pregnancies

The investigator should report pregnancies in female study subjects that are identified after initiation of study drug and throughout the study, including the post study drug follow-up period, to Gilead DSPH using the pregnancy report form within 24 hours of becoming aware of the pregnancy.

Refer to Section [7.3](#) and the eCRF completion guidelines for full instructions on the mechanism of pregnancy reporting.

The pregnancy itself is not considered an AE nor is an induced elective abortion to terminate a pregnancy without medical reasons.

Any premature termination of pregnancy (eg, a spontaneous abortion, an induced therapeutic abortion due to complications or other medical reasons) must be reported within 24 hours as an SAE. The underlying medical reason for this procedure should be recorded as the AE term.

A spontaneous abortion is always considered to be an SAE and will be reported as described in Sections 7.1.1 and 7.1.2. Furthermore, any SAE occurring as an adverse pregnancy outcome post study must be reported to Gilead DSPH.

The subject should receive appropriate monitoring and care until the conclusion of the pregnancy. The outcome should be reported to Gilead DSPH using the pregnancy outcome report form. If the end of the pregnancy occurs after the study has been completed, the outcome should be reported directly to Gilead DSPH. Gilead DSPH contact information is as follows: Email: [contact] and [contact].

Refer to [Appendix 4](#) for Pregnancy Precautions, Definition for Female of Childbearing Potential, and Contraceptive Requirements.

7.6.2.2. Reporting Other Special Situations

All other special situation reports must be reported on the special situations report form and forwarded to Gilead DSPH within 24 hours of the investigator becoming aware of the situation. These reports must consist of situations that involve study drug and/or Gilead concomitant medications, but do not apply to non-Gilead concomitant medications.

Special situations involving non-Gilead concomitant medications does not need to be reported on the special situations report form; however, for special situations that result in AEs due to a non-Gilead concomitant medication, the AE should be reported on the AE form.

Any inappropriate use of concomitant medications prohibited by this protocol should not be reported as “misuse,” but may be more appropriately documented as a protocol deviation.

Refer to Section 7.3 and the eCRF completion guidelines for full instructions on the mechanism of special situations reporting.

All clinical sequelae in relation to these special situation reports will be reported as AEs or SAEs at the same time using the AE eCRF and/or the SAE report form. Details of the symptoms and signs, clinical management, and outcome will be reported, when available.

8. STATISTICAL CONSIDERATIONS

8.1. Analysis Objectives and Endpoints

8.1.1. Analysis Objectives

The primary objectives of this study are as follows:

- To determine the efficacy of treatment with SOF/VEL/VOX FDC for 12 weeks as measured by the proportion of subjects with sustained viral response 12 weeks after cessation of treatment (SVR12)
- To evaluate the safety and tolerability of treatment with SOF/VEL/VOX FDC

The secondary objectives of this study are as follows:

- To determine the proportion of subjects who attain SVR at 4 weeks after cessation of treatment (SVR4)
- To evaluate the proportion of subjects with virologic failure
- To evaluate the kinetics of circulating HCV RNA during treatment and after cessation of treatment
- To evaluate the emergence of viral resistance to SOF, VEL, and VOX during treatment and after cessation of treatment

8.1.2. Primary Endpoint

The primary efficacy endpoint is SVR12 in the Full Analysis Set (FAS) population.

8.1.3. Secondary Endpoint

Secondary endpoints include the following:

- SVR4
- The proportion of subjects with HCV RNA < LLOQ on treatment
- The proportion of subjects with virologic failure
- HCV RNA change from Baseline/Day 1

8.1.4. Safety Endpoint

The primary safety endpoint is any AE leading to permanent discontinuation of study drug.

8.2. Analysis Conventions

All individual subject data will be listed as measured. All statistical summaries and analyses will be performed using SAS software (SAS Institute, Cary, North Carolina, USA).

All continuous endpoints will be summarized using an 8-number summary (n, mean, standard deviation [SD], median, 1st quartile [Q1], 3rd quartile [Q3], minimum, maximum). All categorical endpoints will be summarized by the number and percentage of subjects who meet the endpoint definition.

Last dose of study drug refers to the last dose of SOF/VEL/VOX FDC and will be used in the definition of treatment-emergent AEs and laboratory abnormalities as well as the efficacy endpoints of SVR at various post-treatment time points.

8.2.1. Analysis Sets

8.2.1.1. Efficacy

The analysis set for efficacy analyses will be the FAS, which includes all enrolled subjects who took at least 1 dose of the study drug.

8.2.1.2. Safety

The analysis set for safety analyses will include subjects who received at least one dose of study drug.

Treatment-emergent data will be analyzed and defined as data collected from the first dose of the study drug through the last dose date of the study drug plus 30 days.

8.3. Data Handling Conventions

Missing data can have an impact upon the interpretation of the trial data. Other than the endpoints discussed below, values for missing data will not be imputed.

For the analyses of categorical HCV RNA data, missing posttreatment HCV RNA data will have the missing data imputed. Missing on-treatment HCV RNA will have the missing data imputed up to the time of the last dose.

If a data point is missing and is preceded and followed in time by values that are “< LLOQ target not detected (TND),” then the missing data point will be set to “< LLOQ TND.” If a data point is missing and preceded and followed by values that are “< LLOQ detected,” or preceded by “< LLOQ detected” and followed by “< LLOQ TND,” or preceded by “< LLOQ TND” and followed by “< LLOQ detected,” then the missing value will be set to “< LLOQ detected.” In these situations the data point will be termed a bracketed success; otherwise, the data point will be termed a bracketed failure (i.e., \geq LLOQ detected). If a data point is missing and is not bracketed, the missing data point will also be termed a failure (i.e., \geq LLOQ detected).

Where appropriate, safety data for subjects who did not complete the study will be included in summary statistics. For example,

- If a subject took at least 1 dose of study drug, the subject will be included in a summary of AEs according to the treatment received; otherwise, if the subject is not dosed, then they will be excluded from the summary.
- If safety laboratory results for a subject are missing for any reason at a time point, the subject will be excluded from the calculation of the summary statistics for that time point. If the subject is missing a predose value, then the subject will be excluded from the calculation of the summary statistics for the predose value and the change from predose values.

Values for missing safety laboratory data will not be imputed; however, a missing Baseline/Day 1 result will be replaced with a screening result, if available. If no pretreatment laboratory value is available, the Baseline/Day 1 value will be assumed to be normal (i.e., no grade [Grade 0]) for the summary of graded laboratory abnormalities.

Values for missing vital signs data will not be imputed; however, a missing Baseline/Day 1 result will be replaced with a screening result, if available.

HCV RNA values below the LLOQ for the assay will be set to the lower limit minus 1 for the calculation of summary statistics for the actual HCV RNA values and the change from baseline values by study visit. The reported values will be provided in the HCV RNA listing.

For selected analyses of early time point data, HCV RNA data (IU/mL) may be transformed to the logarithmic (base 10) scale (\log_{10} IU/mL).

8.4. Demographic Data and Baseline Characteristics

Demographic and baseline measurements will be summarized using standard descriptive methods

Demographic data will include sex, self-identified race/ethnicity, and age. Baseline characteristic data will include body mass index, HCV RNA level (\log_{10} IU/mL), genotype of HCV infection, IL28B genotype, and additional endpoints as necessary.

8.5. Efficacy Analysis

8.5.1. Primary Analysis

The primary efficacy endpoint is SVR12 (HCV RNA < LLOQ 12 weeks after cessation of treatment) in the FAS population. The primary analysis will be performed after all enrolled subjects have been followed through 12 weeks posttreatment or discontinued from study.

A point estimate with a two-sided 95% exact confidence interval using the binomial distribution (Clopper-Pearson method) {[Clopper 1934](#)} will be constructed for the SVR12 for the FAS.

8.5.2. Secondary Analyses

The proportion of subjects with HCV RNA below the LLOQ over time (including SVR endpoints) will be presented in tabular and graphical form.

Descriptive summaries and listings will be provided for additional efficacy evaluations of the proportion of subjects who experience virologic failure, HCV RNA actual values and change from baseline.

8.5.3. Exploratory Analysis

PPD

PPD

8.6. Safety Analysis

Safety will be evaluated by assessment of clinical laboratory tests, physical examinations, vital signs measurements at various time points during the study, and by the documentation of AEs.

All safety data collected on or after the first dose of study drug administration up to 30 days after the last dose of study drug will be summarized.

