6.4. Post-treatment Assessments (\pm 5 days)

The posttreatment Week 4 and 12 visits should be timed from the date of last dose of study drug. All subjects will complete the posttreatment Week 4 and 12 visits.

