7.2.2. Assessment of Severity

The severity grading of AEs will be assessed as Grade 1, 2, 3, or 4 using the GSI Grading Scale for Severity of Adverse Events and Laboratory Abnormalities ([Appendix 3](#)). For AEs associated with laboratory abnormalities, the event should be graded on the basis of the clinical severity in the context of the underlying conditions; this may or may not be in agreement with the grading of the laboratory abnormality.

7.3. Investigator Requirements and Instructions for Reporting Adverse Events and Serious Adverse Events to Gilead

Requirements for collection prior to study drug initiation:

After informed consent, but prior to initiation of study medication, the following types of events should be reported on the eCRF: all SAEs and AEs related to protocol-mandated procedures.

A subject's treatment history is a pre-requisite for entry into the study (eg, lack of effect of a prior Gilead product for the treatment of HCV); this will not be recorded on a Special Situations Report (SSR).

Adverse Events:

Following initiation of study drug, collect all AEs, regardless of cause or relationship, special situation reports, and pregnancy reports until 30 days after last dose of study drug.

All AEs should be followed up until resolution or until the AE is stable, if possible. Gilead Sciences may request that certain AEs be followed beyond the protocol defined follow-up period.

Serious Adverse Events:

All SAEs, regardless of cause or relationship, that occurs after the subject first consents to participate in the study (i.e., signing the informed consent) and throughout the duration of the study, including the protocol-required posttreatment follow-up period, must be reported to the eCRF database and Gilead Drug Safety and Public Health (DSPH) as instructed. This also includes any SAEs resulting from protocol-associated procedures performed after informed consent is signed.

Investigators are not obligated to actively seek SAEs after the protocol defined follow up period however, if the investigator learns of any SAEs that occur after study participation has concluded and the event is deemed relevant to the use of study drug, he/she should promptly document and report the event to Gilead DSPH.

All AEs and SAEs will be recorded in the eCRF database within the timelines outlined in the eCRF completion guideline.

Electronic Serious Adverse Event (eSAE) Reporting Process

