8.6.2. Adverse Events

Clinical and laboratory AEs will be coded using the Medical Dictionary for Regulatory Activities (MedDRA). System Organ Class (SOC), High-Level Group Term (HLGT), High-Level Term (HLT), Preferred Term (PT), and Lower-Level Term (LLT) will be attached to the clinical database.

Events will be summarized on the basis of the date of onset for the event. A treatment-emergent AE will be defined as any AE with an onset date on or after the study drug start date and no later than 30 days after permanent discontinuation of the study drug; or any AE leading to premature discontinuation of the study drug.

Summaries (number and percentage of subjects) of treatment-emergent AEs (by SOC and PT) will be provided:

- All AEs
- AEs of Grade 3 or above
- AEs of Grade 2 or above
- All treatment-related AEs
- Treatment-related AEs of Grade 3 or above
- Treatment-related AEs of Grade 2 or above
- All SAEs (including death)
- All treatment-related SAEs
- All AEs leading to premature discontinuation of the study drug

All AEs collected during the study will be presented in the data listings.

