Appendix 2. Study Procedures Table

	Screen ^a	Day 1 ^b	On-Treatment Study Week (±3 Days)					Posttreatment Study Week (±5 Days)	
			2	4	8	12/EoT	ET	4	12
Informed Consent	X								
Determine Eligibility	X	X							
Medical History	X								
Physical Examination	X	X				X	X		
Height	X								
Weight	X	X							
Vital Signs	X	X	X	X	X	X	X	X	
12-Lead ECG	X						X		
Imaging for HCC ^c	X								
AEs/ SAEs	X	X	X	X	X	X	X	X	X ^d
Concomitant Medications	X	X	X	X	X	X	X	X	
Review of Study Drug Compliance (Pill Count)			X	X	X	X	X		
Study Drug Dispensing		X		X	X				
Hematology, Chemistry	X	X	X	X	X	X	X	X	
Coagulation Tests	X	X				X	X		
HCV RNA	X	X	X	X	X	X	X	X	X
HBV DNA ^e				X	X	X	X	X	X
Viral Sequencing/phenotyping ^f		X	X	X	X	X	X	X	X
Pregnancy Testing ^g	X	X		X	X	X	X	X	

	Screen ^a	Day 1 ^b	On-Treatment Study Week (±3 Days)					Posttreatment Study Week (±5 Days)	
			2	4	8	12/EoT	ET	4	12
Urinalysis, Urine Drug Screen	X								
HCV Genotyping ^h , IL28B	X								
HCV, HIV, HBV Serology	X								
HbA1c, Fibrotest [®]	X								
PPD									
Single PK Sample			X	X	X	X	X		

- a Screening assessments to be completed within 28 days of the Day 1 visit. The screening window can be extended to 42 days for subjects requiring a liver biopsy, or for extenuating circumstances with sponsor approval.
- b Day 1 assessments must be performed prior to dosing.
- c Cirrhotic subjects will have liver imaging within 6 months of Day 1 to exclude HCC.
- d Only SAEs will be collected at the posttreatment week 12 visit.
- e Only for subjects who are HBcAb+ at Screening.
- f Plasma will be collected for possible viral resistance or other virology studies.
- g For females of childbearing potential only: serum β-hCG at Screening, urine pregnancy testing will occur every 4 weeks during the dosing period and for 30 days following the last dose of study drug.
- h HCV genotyping to be performed by the central laboratory utilizing the LiPa assay.

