7.1.6. Summaries of Adverse Events and Deaths

A brief high-level summary of TEAEs will be provided by the number and percentage of subjects who had the following: any AE; any AE of Grade 3 or above; any AE of Grade 2 or above; any treatment-related AE; any treatment-related AE of Grade 3 or above; any treatment-related AE of Grade 2 or above; any SAE; any treatment-related SAE; any AE that led to premature discontinuation of study drug. All deaths (including those that are treatment emergent and those that are not treatment emergent) observed during the study will also be summarized and included in this table.

Adverse event summaries will provide the number and percentage of subjects with TEAEs by SOC and PT based on the Safety Analysis Set as follows:

- All AEs
- AEs of Grade 3 or above
- AEs of Grade 2 or above
- All treatment-related AEs
- Treatment-related AEs of Grade 3 or above
- Treatment-related AEs of Grade 2 or above
- All SAEs
- All treatment-related SAEs
- All AEs leading to premature discontinuation of study drug
- All AEs leading to interruption of study drug
- Deaths

Multiple events will be counted only once per subject in each summary. Adverse events will be summarized and listed first in alphabetic order of SOC and then by PT in order of descending incidence within each SOC. In summaries by severity grade, the most severe grade will be used for those AEs that occurred more than once in an individual subject during the study.

In addition to the above summary tables, TEAEs will be summarized by PT only, in order of descending incidence for:

- AEs that occurred in at least 5% of subjects
- AEs of Grade 3 or above
- All treatment-related AEs
- All SAEs
- AEs leading to premature discontinuation of study drug
- All AEs leading to interruption of study drug

In addition to the summaries described above, data listings will be provided for the following:

- All AEs (with a variable indicating whether the event is treatment emergent)
- AEs of Grade 3 or above
- SAEs
- Deaths
- AEs leading to premature discontinuation of study drug

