Appendix 1. Study Procedures Table

	Screen ^a	Day 1 ^b	On-Treatment Study Week (±3 Days)					Posttreatment Study Week (±5 Days)	
			2	4	8	12/EoT	ET	4	12
Informed Consent	X								
Determine Eligibility	X	X							
Medical History	X								
Physical Examination	X	X				X	X		
Height	X								
Weight	X								
Vital Signs	X	X	X	X	X	X	X	X	
12-Lead ECG	X						X		
Imaging for HCC ^c	X								
AEs/ SAEs ^h	X	X	X	X	X	X	X	X	X ^h
Concomitant Medications	X	X	X	X	X	X	X	X	
Review of Study Drug Compliance (Pill Count) ^d			X	X	X	X	X		
Study Drug Dispensing		X		X	X				
Hematology, Chemistry	X	X	X	X	X	X	X	X	
Coagulation Tests	X	X				X	X		
HCV RNA	X	X	X	X	X	X	X	X	X
HBV DNA ⁱ				X	X	X	X	X	X
Viral Sequencing/phenotyping ^d		X	X	X	X	X	X	X	X
Pregnancy Testing ^e	X	X		X	X	X	X	X	

	Screen ^a	Day 1 ^b	On-Treatment Study Week (±3 Days)					Posttreatment Study Week (±5 Days)	
			2	4	8	12/EoT	ET	4	12
Urinalysis, Urine Drug Screen	X								
HCV Genotyping ^f , IL28B	X								
HCV, HIV, HBV Testing	X								
HbA1c, Fibrotest [®]	X								
Archive Plasma Sample ^g		X				X	X		
Single PK Sample			X	X	X	X	X		

- a. Screening assessments to be completed within 28 days of the Day 1 visit. The screening window can be extended to 42 days for subjects requiring a liver biopsy, or for extenuating circumstances with sponsor approval.
- b. Day 1 assessments must be performed prior to dosing
- c. Cirrhotic subjects will have liver imaging within 6 months of Day 1 to exclude HCC.
- d. Plasma will be collected for possible viral resistance or other virology studies.
- e. For females of childbearing potential only: serum β-hCG at Screening, urine pregnancy testing will occur every 4 weeks during the dosing period and for 30 days following the last dose of study drug.
- f. HCV genotyping to be performed by the central laboratory utilizing the LiPa assay.
- g. Subjects may opt out of archive sample collection.
- h. Only SAEs will be collected at post-treatment week visits.
- i. Only for subjects who are HBcAb+ at Screening.

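### SAEs are collected to posttreatment Week 12 but counted only to 30 days after the last dose, so a later nonfatal SAE appears in listings and in no count or percentage, while the same table counts deaths throughout the study

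*Protocol*

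**What the plan says.** **Collection.** Protocol 7.3 requires SAEs, whatever their cause, to be reported from consent onward: those occurring "throughout the duration of the study, including the protocol-required posttreatment follow-up period, must be reported to the eCRF database". Footnote d of Protocol Appendix 2 confirms the last contact: "Only SAEs will be collected at the posttreatment week 12 visit". Other adverse events stop earlier; Protocol 7.3 has sites "collect all AEs, regardless of cause or relationship, special situation reports, and pregnancy reports until 30 days after last dose of study drug". The matching footnote in SAP Appendix 1 is worded more broadly ("Only SAEs will be collected at post-treatment week visits"), but it agrees that SAEs are still sought at Week 12.

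**Counting.** Protocol 8.6 plans summaries of safety data from the "first dose of study drug administration up to 30 days after the last dose of study drug will be summarized". Protocol 8.6.2 then lists its tables, including the one beginning "All SAEs (including death", as summaries of treatment-emergent events. SAP 7.1.6 does the same for the high-level table, the tables by system organ class and preferred term, and the tables by preferred term alone. SAP 7.1.5.1 defines treatment-emergent as onset within 30 days of stopping drug, or an event that led to premature discontinuation.

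**Deaths.** SAP 7.1.6 makes one exception, in the high-level table: "All deaths (including those that are treatment emergent and those that are not treatment emergent) observed during the study will also be summarized".

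**Listings.** Protocol 8.6.2 and SAP 7.1.6 list all adverse events. The SAP listing flags whether each is treatment-emergent, and there is a separate SAE listing.

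**The concern.** Safety and tolerability is a primary objective, and the study has one arm and no data monitoring committee. The descriptive counts are therefore its main quantitative safety result. After the 30-day point, SAEs are the only adverse event category the protocol still asks sites to collect in full, yet no planned table counts a nonfatal one. The protocol does look for late harm: section 6.7.10 continues HBV DNA testing to posttreatment Week 12 in subjects who are hepatitis B core antibody positive, to monitor for reactivation.

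Two consequences follow. The planned SAE percentage covers a shorter period than the one over which SAEs were collected, and nothing beside it gives the full-study figure. In addition, rows of one high-level table cover different periods. A subject who dies of an event that began after day 30 would be counted in the deaths row without that event entering the SAE row.

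**Working it through.** **Inputs**

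- Treatment: 12 weeks = 84 days (Protocol 3.3).
- Posttreatment follow-up: 12 weeks = 84 days from last dose. Protocol 6.4: "The posttreatment Week 4 and 12 visits should be timed from the date of last dose of study drug". The visit window is ±5 days (Protocol 6.4, Appendix 2).
- Cut-off for counts: last dose + 30 days (Protocol 8.6, 8.6.2; SAP 7.1.5.1).
- Planned size: about 50 subjects (SAP 1.3).

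**Step 1: reproduce the plan's own figure.** SAP 1.2 gives about 30 weeks in total. Screening 6 + treatment 12 + follow-up 12 = 30 weeks, so the follow-up length is confirmed.

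**Step 2: length of the uncounted interval.**

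| Day of Week 12 visit after last dose | Uncounted days | Share of posttreatment follow-up |
|---|---|---|
| 79 | 79 − 30 = 49 | 49/79 = 62.0% |
| 84 (nominal) | 84 − 30 = 54 | 54/84 = 64.3% |
| 89 | 89 − 30 = 59 | 59/89 = 66.3% |

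From first dose, nominal collection lasts 84 + 84 = 168 days and the counts cover 84 + 30 = 114. The uncounted share is 54/168 = 32.1%.

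**Step 3: does any rule bring a late SAE into a count?**

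- The discontinuation limb of the treatment-emergent definition does not help: an event that starts more than 30 days after the last dose cannot have caused drug to be stopped early.
- Relatedness does not help: the treatment-related SAE tables are also limited to treatment-emergent events.
- The incomplete-date rule (SAP 7.1.5.2) can class an SAE with a partial or missing onset date as treatment-emergent although it began later. The point therefore applies to SAEs with a known onset.
- The exception for deaths puts a late death in the deaths row. It does not put it in an SAE row.

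**Step 4: how often this might matter (illustration only).** The documents give no rate of late SAEs. For an assumed risk r of a nonfatal SAE in the 54 days, among 50 subjects, the expected number uncounted is 50r and the chance of at least one is 1 − (1 − r)^50.

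| Assumed r | Expected uncounted | Chance of at least one |
|---|---|---|
| 0.5% | 0.25 | 22% |
| 1% | 0.5 | 40% |
| 2% | 1.0 | 64% |
| 5% | 2.5 | 92% |

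One subject is 1/50 = 2 percentage points.

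**The case against.** The strongest reply is that nothing here is a mistake. The 30-day window is applied consistently in both documents, to laboratory data as well as adverse events. Collecting SAEs for longer than the treatment-emergent window is not a contradiction. Late SAEs are reported by subject, with a flag, and with so few expected in about 50 subjects a listing conveys most of what a count would. The tables are already introduced as summaries of treatment-emergent events. The primary safety endpoint, an adverse event leading to permanent discontinuation (Protocol 8.1.4), is unaffected, and no test or stopping decision depends on an SAE percentage.

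Most of that stands, and it rules out several stronger readings that a reader might infer:

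- *That late SAEs are lost or hidden.* They are not; the gap is in counts and percentages.
- *That the 30-day definition is wrong, or that the collection and analysis sections contradict each other.* The documents do not support this.
- *That a late death enters an SAE count while a late nonfatal SAE does not.* It enters only the deaths row. The protocol's SAE table that mentions death is itself limited to treatment-emergent events.
- *That the probabilities above estimate what will happen.* They rest on assumed rates. Protocol 1.2.2 describes SAEs with this regimen as few or of low incidence, which argues against relying on the upper end.
- *That a third of all SAE collection time is uncounted.* The 32% is measured from first dose. Measured from consent, with the maximum 42-day screening, it is 54/(42 + 168) = 54/210 = 26%.

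What the reply leaves unanswered is that no summary gives the number of subjects with any SAE during the study, or with any drug-related SAE, although the data exist and the SAP saw reason to go past the window for deaths.

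**Conclusion.** The point holds as a reporting gap of minor severity. A nonfatal SAE with a known onset in the last nominal 54 days of follow-up (49 to 59 with the visit window) would be visible in listings and absent from every planned count and percentage, whatever its relation to drug. The high-level table would place that shorter SAE window beside an all-study count of deaths. The day counts follow from the documents and assume that subjects attend the Week 12 visit within its window. The likelihood of an uncounted SAE cannot be determined from the documents. The SVR12 analysis and the primary safety endpoint are not affected.

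**What to change.** Keep the treatment-emergent definition and every planned table. In the SAP 7.1.6 high-level table:

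1. Label the SAE rows that stop at 30 days as treatment-emergent.
2. Next to the deaths row, add *any SAE, first dose to end of study* and *any treatment-related SAE, first dose to end of study*, each with n and % of the Safety Analysis Set.

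Amend the sentence in Protocol 8.6 so that SAEs and deaths may be summarized to the end of the study. If only the SAP is changed, record the addition in SAP 7.7, which now states that there are no departures from the protocol's safety analyses.

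With these rows, the posttreatment days covered by an SAE count rise from 30 of 84 to 84 of 84, and a subject with a late fatal SAE is counted in both places. The cost is two rows computed from data already collected. The downside is that the all-study SAE percentage may be slightly higher than the treatment-emergent one. Settling this before the database is finalized avoids an ad hoc decision if a late SAE occurs.
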